3.2 End of Study

The End of Study is considered the date on which the last patient randomized completes the visit on Day 60, unless CalciMedica terminates the study early.

3.3 Sponsor Termination of the Study

CalciMedica intends to complete the study as outlined. CalciMedica reserves the right, however, to terminate the study at any time or for any reason including:

- A directive from the FDA
- A lack of enrollment
- A recommendation from the IDMC

4 SELECTION OF PATIENTS

4.1 Inclusion Criteria

All of the following must be met for a patient to be randomized into the study:

1. Has laboratory-confirmed SARS-CoV-2 infection as determined by polymerase chain reaction (PCR) or other commercial or public health assay in any specimen;
2. Moderate ARDS characterized by the following criteria:
 - o Invasive mechanical ventilation with a minimum PEEP of 5 cm H₂O;
 - o PaO₂/FiO₂ ≤200 that may be estimated pulse oximetry or determined by arterial blood gas;
 - o No evidence of volume overload or heart failure as the sole cause of pulmonary edema;
3. The patient is ≥18 years of age;
4. QTcF interval ≤440 milliseconds;
5. A female patient of childbearing potential must not attempt to become pregnant for 39 months, and if sexually active with a male partner, is willing to practice acceptable methods of birth control for 39 months after the last dose of study drug;
6. A male patient who is sexually active with a female partner of childbearing potential is willing to practice acceptable methods of birth control for 39 months after the last dose of study drug. A male patient must not donate sperm for 39 months;
7. The patient is willing and able to, or has a legal authorized representative (LAR) who is willing and able to, provide informed consent to participate, and to cooperate with all aspects of the protocol.

4.2 Exclusion Criteria

Patients with any of the following conditions or characteristics must be excluded from randomizing:

1. Expected survival or time to withdrawal of life-sustaining treatments expected to be <7 days;
2. ECMO;
3. Invasive mechanical ventilation for more than 7 days
4. Suspected septic shock;
5. The patient has a history of:
 - a. Organ or hematologic transplant;
 - b. HIV;
 - c. Active hepatitis B, or hepatitis C infection;

6. Current treatment with:
 - a. Chemotherapy;
 - b. Immunosuppressive medications or immunotherapy (see [Section 5.3](#) for list of prohibited immunosuppressive medications and immunotherapy) at the time of consent;
 - c. Hemodialysis or Peritoneal Dialysis;
7. The patient is known to be pregnant or is nursing;
8. Currently participating in another study of an investigational drug or therapeutic medical device at the time of consent;
9. Allergy to eggs or any of the excipients in Auxora.

4.3 Re-Screening

A patient who fails the initial screening may be rescreened twice again within 24 hours of the original screening.

5 TREATMENT OF PATIENTS

5.1 Overview

All patients enrolled in the study should receive care consistent with local standard of care including for ventilator management. Patients should receive conservative intravenous fluid strategies such as FACTT LITE. All patients should receive pharmacological prophylaxis to prevent the development of venous thromboembolic disease. The type and dose of prophylaxis should be determined by local standard of care.

Patients enrolled in the study should receive dexamethasone as standard of care. If patients are not receiving dexamethasone at the time of randomization, starting dexamethasone during the hospitalization should be considered. If the patient is already receiving dexamethasone at the time of randomization, dexamethasone should be continued on its established dosing schedule. The COVID-19 Treatment Guidelines Panel of the National Institutes of Health recommends using dexamethasone (at a dose of 6 mg per day, given orally or intravenously, for up to 10 days) in patients with COVID-19 who require supplemental oxygen. Before initiating dexamethasone, the potential risks and benefits of administering corticosteroids should be assessed including risks for hyperglycemia and secondary infections. At this time, it is not known whether other corticosteroids, such as prednisone, methylprednisolone, or hydrocortisone, will have a similar benefit to dexamethasone. Of note, the dose equivalencies for dexamethasone 6 mg daily are prednisone 40 mg, methylprednisolone 32 mg, and hydrocortisone 160 mg.

If patients are not receiving remdesivir at the time of randomization, starting remdesivir during the hospitalization may be considered. If the patient is already receiving remdesivir at the time of randomization, remdesivir should be continued on its established dosing schedule. The suggested dose of remdesivir for adults weighing ≥ 40 kg and not requiring invasive mechanical ventilation and/or ECMO is a single dose of 200 mg infused intravenously over 30 to 120 minutes on Day 1 followed by once-daily maintenance doses of 100 mg infused intravenously over 30 to 120 minutes for 4 days (days 2 through 5). If a patient does not demonstrate clinical improvement, treatment may be extended for up to 5 additional days (i.e., up to a total of 10 days). Auxora and remdesivir should not be infused at the same time but should be given sequentially.

Patients may also be considered for the administration of convalescent plasma in the study as per local standard of care.

Immunosuppressive medications or immunotherapies are prohibited in patients randomized into the study (see [Section 5.3](#) for the list of prohibited medications). The use of dextromethorphan in patients is discouraged when enrolled in the study.

5.2 Discharge Criteria

Patients should remain in the hospital until all doses of study drug have been administered.

If the patient is ready to be discharged before all doses of study drug have been administered, the PI or treating physician should contact the Medical Monitor prior to discharging the patient.

5.3 Prohibited Medications

Any medication, with the exception of those listed below, may be given at the discretion of the PI. Medications that should not be administered during the study to patients randomized in the study include:

- Chemotherapy
- Cyclosporine, Tacrolimus
- Sirolimus, Everolimus
- Azathioprine
- Cyclophosphamide
- Methotrexate
- Mycophenolate
- Leflunomide
- Biologics/Monoclonals: abatacept, adalimumab, alemtuzumab, anakinra, basilizimab, belimumab, bevacizumab, brodalumab, canakinumab, certolizumab, cetuximab, clazakizumab, daclizumab, eculizumab, etanercept, golimumab, infliximab, interferon, ixekizumab, muromonab, natalizumab, omalizumab, rituximab, sarilumab, secukinumab, trastuzumab, ustekinumab, vedolizumab
- Baricitinib
- Tofacitinib

5.4 Compliance

Only the PI or his/her appropriately trained study staff will administer study drug to patients randomized in the trial in accordance with the protocol. Study drug must not be used for any reasons other than that described in the protocol.

6 PROCEDURES

6.1 Enrollment Procedures

Up to 32 patients will be enrolled in the study sequentially into three cohorts. If a patient discontinues study drug, withdraws consent, gets extubated or dies before the second BAL is performed, they will be replaced by the enrollment of an additional patient in the cohort.

6.2 Discontinuation and Withdrawal

The term discontinuation refers to a patient or PI discontinuing the administration of study drug before all doses are administered despite the patient remaining in the hospital. Patients who do not receive all doses because the treating physician discharged them from the hospital will not be considered to have discontinued study medication.

Patients have the right to discontinue the administration of study drug at any time for any reason, without prejudice to their medical care. The PI may discontinue the administration of study drug because of an adverse event or change in medical status that raises a safety concern about the patient receiving additional doses of study drug. The PI **must** discontinue the administration of study drug if the patient is diagnosed with a new or recurrent malignancy. If possible, the PI should contact the Medical Monitor to review the reasons for a patient's discontinuation from study drug. The PI should also record the reason for the discontinuation in the eCRF and appropriate source documents at the site. Even if the patient discontinues receiving study drug, diligence should occur to ensure that all study visits and assessments are completed.

Withdrawal refers only to the complete withdrawal of the patient from the study because of the withdrawal of consent. The PI should inform the Medical Monitor of the withdrawal of consent and record the withdrawal of consent in the eCRF and appropriate source documents at the site.

7 STUDY DRUG MATERIALS AND MANAGEMENT

7.1 Auxora Product Description

Auxora is to be administered as an IV infusion and is supplied as a translucent, white to yellowish, sterile, non-pyrogenic emulsion containing 1.6 mg/mL of the active pharmaceutical ingredient CM4620. Auxora is supplied as a single-use glass vial. Auxora contains egg phospholipids, medium chain triglycerides, glycerin, edetate disodium salt dehydrate (EDTA), sodium hydroxide (as needed to adjust pH), and sterile water for injection (Table 4).

Table 4. Auxora Product Information

Product Name:	CM4620 Injectable Emulsion
Dosage Form:	Injectable Emulsion (Liquid)
Concentration of CM4620	1.6 mg/mL
Route of Administration	IV
Physical Description	Translucent, non-separated, white to yellowish emulsion
Inactive Ingredients	Sterile Water for Injection USP, Egg Phospholipid NF (80% Phosphatidylcholine), Medium Chain Triglycerides NF, Glycerin USP, and Edetate Disodium Salt Dihydrate (EDTA) USP. Sodium Hydroxide and Hydrochloric Acid may be added to adjust the pH.
Manufacturer	Bioserv Corporation San Diego, CA 92121

7.2 Placebo Product Description

Matching Placebo is to be administered as an IV infusion and is supplied as a translucent, white to yellowish, sterile, non-pyrogenic emulsion carrier containing no active pharmaceutical ingredient. Placebo is supplied as an 80 mL fill in a 100 mL single-use vial. Placebo contains the same ingredients as Auxora except that it does not contain CM4620.

7.3 Auxora and Placebo Storage

Auxora and Placebo must be maintained in a secure location with refrigerated temperature conditions of 2 to 8°C (36 to 46°F). Precaution should be taken to ensure that Auxora and the Placebo do not freeze. Temperature logs should be maintained and available during monitor review. When a temperature is noted outside the range of 2°C to 8°C lasting for 24 hours or more, or if the temperature exceeds 20°C (68°F), or is below 0°C (32°F), CalciMedica or its designee must be notified as soon as possible. The stability of Auxora and Placebo has been demonstrated to 24 months and is being evaluated for longer periods in ongoing studies.

7.4 Auxora and Placebo Preparation

The study pharmacist and/or designee will be responsible for the preparation and dispensation of Auxora and Placebo. Prior to administration, Auxora and Placebo both must be transferred to

a sterile container using a sterile technique. Specific details on how to prepare Auxora and Placebo, as well as the specific components that will be used to administer both Auxora and Placebo, will be provided in the Pharmacy Manual. The Pharmacy Manual will also contain tables detailing the selected dose level and volume of administration of Auxora and Placebo.

7.5 Auxora and Placebo Administration

In Cohorts 1, 2, and for the first infusion in Cohort 3, study drug will be administered intravenously as a continuous infusion over 4 hours (\pm 30 minutes). In Cohort 3, after the end of the first infusion, a 96-hour continuous infusion will commence; during the continuous infusion study drug infusion bags will be prepared daily, each diluted up to 500 mL with the addition of normal saline and each for administration continuously over 24 hours (\pm 30 minutes). Study drug will be administered via a bag and tubing compatible with lipid emulsions and using a 1.2-micron filter.

The Start of the First Infusion of Study Drug (SFISD) will be considered 0 hours. In Cohorts 1 and 2, study drug will again be administered at 24 (\pm 2) and 48 (\pm 2) hours from the SFISD. In Cohort 2 study drug will also be administered at 72 (\pm 2) hours from the SFISD. In Cohort 3, study drug will be administered as a continuous infusion for 96 hours after the first infusion of study drug is completed. The dose and volume of Auxora, and the volume of Placebo, that will be administered will be calculated using the patient weight obtained at the time of hospitalization or during screening. A line into a peripheral or central vein may be used for the infusion. The peripheral IV should be 20 gauge in size or larger. The peripheral IV or central line port should be dedicated when administering Auxora or Placebo other than 0.9% normal saline. Auxora and Placebo are compatible with 0.9% normal saline. The IV tubing used to administer Auxora and Placebo must contain a 1.2 micron filter. The Pharmacy Manual will contain a recommended procedure to prime the IV tubing and flush the tubing, but this may be adapted to local nursing standards. 0.9% normal saline may be used to clear the line to ensure that the volume to be infused (VTBI) is completely administered. If the administration of Auxora or Placebo is stopped because of a technical reason, such as failure of the IV site, or IV pump malfunction, the administration of Auxora or Placebo should be resumed when the technical reason is resolved, and continued at the same rate until the infusion is completed. The total amount of time for the start of infusion to end of infusion of Auxora or Placebo should be recorded.

CalciMedica may modify at any time the administered doses of Auxora or volumes of Placebo, the days of infusion, the timing of the infusion and the rate of infusion based on review of the safety and tolerability data by the IDMC. If the administration of Auxora or Placebo is stopped because of a serious adverse event that is considered to be probably or definitely related to Auxora or Placebo, the Medical Monitor must be immediately contacted.

7.6 Packaging and Labeling

Preparation, packaging and labeling of Auxora and Placebo will be in accordance with current Good Manufacturing Practice of Medicinal Products (GMP) guidelines. Medication labels will comply with legal requirements for labeling of investigational products in the United States.

7.7 Accountability, Handling and Disposal

The PI or designee will ensure that deliveries of Auxora and Placebo from CalciMedica or its designee are received by a responsible person, and such deliveries are recorded; that Auxora and Placebo are handled and stored safely and properly; that Auxora and Placebo are only dispensed to study patients in accordance with the protocol; and that unused Auxora and Placebo is returned to CalciMedica or its designee or disposed of using standard procedures approved of in advance by CalciMedica or its designee. Appropriately trained study staff will administer all doses of Auxora and Placebo. The pharmacy will maintain a record of Auxora and Placebo accountability.

8 VISITS AND STUDY SPECIFIC ASSESSMENTS

8.1 Screening

The PI or designee must provide informed consent to the patient, or LAR, allowing the patient or LAR adequate time to consider, ask questions and receive answers, prior to agreeing to participate.

- Record the time of the patient or LAR provides informed consent

After informed consent is obtained, the following procedures are to be performed:

- Record vital signs closest to the time of assessment
- Record height and weight closest to the time of assessment
- Record results of Sars-CoV-2 testing
- Record the P/F ratio (-4 hours); it may be estimated from pulse oximetry or determined by arterial blood gas closest to the time of assessment
- Perform ECG and record QTcF interval
- Obtain serum pregnancy test in WOCBP

If the patient satisfies all of the inclusion criteria and none of the exclusion criteria, proceed to baseline assessment.

8.2 Baseline Assessment

- Draw blood samples for laboratory monitoring
- Perform the BAL and obtain fluid for flow cytometry, single cell RNA sequencing, biomarker/chemokine panel, SARS-CoV-2 PCR
- Obtain blood for biomarkers/chemokines at the time of the BAL

These blood tests for laboratory monitoring may be performed on blood already drawn in the previous 12 hours prior to randomization or after randomization but prior to the start of the first infusion of study drug. After performing procedures, proceed to randomization.

8.3 Randomization

- Randomize patient as per study randomization procedure.

8.4 Start of First Infusion of Study Drug (SFISD) 0 hour

Record concomitant medications that were administered in the 24 hours prior to the SFISD:

- **For patients in Cohorts 1, 2, and 3, infuse the first dose of study drug. The SFISD should begin within 8 hours of the patient being randomized**

- Record the time when the infusion of study drug starts and finishes
- At the end of infusion of Auxora, draw blood sample for PK (+30 minutes)
- For patients in Cohort 3, begin the continuous infusion of study drug that will continue for the next 96 hours and ends 100 hours after the SFISD

8.5 24 hours

24 (± 1) hours from the SFISD:

- Record concomitant medications that were being administered in the past 24 hours
- Record vital signs closest to the time of the assessment
- Record the P/F ratio (-4 hours); it may be estimated from pulse oximetry or determined by arterial blood gas closest to the time of the assessment
- Perform ECG and record QTcF interval (-2 hours)
- Perform AE/SAE assessment
- Draw blood sample for laboratory monitoring (-12 hours)
- Draw blood sample for PK prior to the second infusion of Auxora (-2 hours) for patients in Cohort 1 and 2. For patients in Cohort 3, draw blood sample for PK 24 hours from the SFISD (± 2 hours)
- **For patients in Cohorts 1 and 2, start the infusion of second dose of study drug 24 hours (± 1 hour) from the SFISD**
 - Record the time when the infusion of study drug starts and finishes
- For patients in Cohort 3, the continuous infusion is ongoing

8.6 48 hours

48 (± 1) hours from the SFISD:

- Record concomitant medications that were being administered in the past 24 hours
- Record vital signs closest to the time of the assessment
- Record the P/F ratio (-4 hours); it may be estimated from pulse oximetry or determined by arterial blood gas closest to the time of the assessment
- Perform ECG and record QTcF interval (-2 hours)
- Perform AE/SAE assessment
- Draw blood samples for laboratory monitoring (-12 hours)
- Draw blood sample for PK prior to third infusion of Auxora (-2 hours) for patients in Cohort 1 and 2. For patients in Cohort 3, draw blood sample for PK 48 hours from the SFISD (± 2 hours)

- **For patients in Cohorts 1 and 2, start the infusion of third dose of study drug 48 hours (± 1 hour) from the SFISD**
 - Record the time that the infusion of study drug starts and finishes
- For patients in Cohort 3, the continuous infusion is ongoing.

8.7 72 hours

72 (± 2) hours from the SFISD:

- Perform BAL on patients randomized to Cohort 1 (± 12 hours)
- At time of BAL, obtain blood for biomarkers and SARS-CoV-2 PCR in patients randomized to Cohort 1 (± 12 hours)
- Perform BAL on patients randomized to Cohort 3 during the final 24 hours of the continuous infusion (between 76 and 100 hours after the SFISD). At the time of BAL, obtain blood for biomarkers and SARS-CoV-2 PCR in patients randomized to Cohort 3.
- Record concomitant medications that were being administered in the past 24 hours
- Record vital signs closest to the time of the assessment
- Record the P/F ratio (-4 hours); it may be estimated from pulse oximetry or determined by arterial blood gas closest to the time of the assessment
- Perform ECG and record QTcF interval (-2 hours)
- Perform AE/SAE assessment
- Draw blood samples for laboratory monitoring (-12 hours)
- In patients randomized to Cohort 2 draw blood sample for PK (-2 hours) prior to infusion of Auxora. For patients in Cohort 3, draw blood sample for PK 72 hours from the SFISD (± 2 hours)
- **In patients randomized to Cohort 2, start the infusion of fourth dose of study drug 72 hours (± 1 hour) from the SFISD**
 - Record the time that the infusion of study drug starts and finishes
- For patients in Cohort 3, the continuous infusion is ongoing.

8.8 96 hours

96 (± 2) hours from the SFISD :

- Perform BAL on patients randomized to Cohort 2 (± 12 hours)
- At time of BAL, obtain blood for biomarkers and SARS-CoV-2 PCR in patients randomized to Cohort 2 (± 12 hours)

- Perform BAL on patients randomized to Cohort 3 during the final 24 hours of the continuous infusion (between 76 and 100 hours after the SFISD). At the time of BAL, obtain blood for biomarkers and SARS-CoV-2 PCR in patients randomized to Cohort 3.
- Record concomitant medications that were being administered in the past 24 hours
- Record vital signs closest to the time of the assessment
- Record the P/F ratio (-4 hours); it may be estimated from pulse oximetry or determined by arterial blood gas closest to the time of the assessment
- Perform ECG and record QTcF interval (-2 hours)
- Perform AE/SAE assessment
- Draw blood samples for laboratory monitoring (-12 hours)
- For patients in Cohort 3 receiving Auxora, draw blood sample for PK (+30 minutes) at the end of the continuous infusion (anticipated at 100 hours (+30 mins) after SFISD)

8.9 120 hours

120 (± 2 hours) from the SFISD:

- Record concomitant medications that were administered in the past 24 hours
- Record vital signs closest to the time of assessment
- Record the P/F ratio (-4 hours); it may be estimated from pulse oximetry or determined by arterial blood gas closest to the time of the assessment
- Perform ECG and record QTcF interval (-2 hours)
- Perform AE/SAE assessment
- Draw blood samples for laboratory monitoring (-12 hours)

8.10 144 hours

144 (± 2 hours) from the SFISD:

- Record concomitant medications that were administered in the past 24 hours
- Record vital signs closest to the time of assessment
- Record the P/F ratio (-4 hours); it may be estimated from pulse oximetry or determined by arterial blood gas closest to the time of the assessment
- Perform ECG and record QTcF interval (-2 hours)
- Perform AE/SAE assessment
- Draw blood samples for laboratory monitoring
- Draw blood sample for PK in all patients who received Auxora

8.11 168 hours Until Discharge or Day 30 if Earlier

Every 48 hours starting at 168 hours (± 4 hours) until discharge or Day 30, whichever is earlier:

- Perform AE/SAE assessment
- If patient is extubated, record time and date of extubation
- If patient is discharged, record date of discharge, if patient was discharged to a nursing home or extended care facility, and if patient was requiring supplemental oxygen at discharge

8.12 Day 60 and Day 30

Patients who were discharged before Day 25 will be contacted on Day 30 (± 5 days) for an AE/SAE assessment as well as to determine if they are receiving supplemental oxygen. For patients discharged from the hospital on Days 25-29, the final inpatient safety assessment will substitute for the Day 30 safety and mortality assessment. The Day 30 safety and mortality assessment may be conducted with an HCP.

Patients, who have been discharged from the hospital before Day 55, will be contacted on Day 60 (± 5 days) to determine if they are receiving supplemental oxygen, experienced any symptoms suggestive of long COVID, and developed any SAEs since the Day 30 assessment. The Day 60 assessment will be completed as a final inpatient safety assessment for patients who remain hospitalized or are discharged from the hospital on Days 55-59.

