
The Start of the First Infusion of Study Drug (SFISD) will be considered 0 hours. In Cohorts 1 and 2, study drug will again be administered at 24 (± 2) and 48 (± 2) hours from the SFISD. In Cohort 2 study drug will also be administered at 72 (± 2) hours from the SFISD. In Cohort 3, study drug will be administered as a continuous infusion for 96 hours after the first infusion of study drug is completed.
 
In Cohorts 1, 2, and for the first infusion in Cohort 3, study drug will be administered intravenously as a continuous infusion over 4 hours (± 30 minutes). In Cohort 3, after the end of the first infusion, a 96-hour continuous infusion will commence; during the continuous infusion study drug infusion bags will be prepared daily, each diluted up to 500 mL with the addition of normal saline and each for administration continuously up to 24 hours (± 30 minutes). Study drug will be administered via a bag and tubing compatible with lipid emulsions and using a 1.2-micron filter.
 
The SFISD should occur within 12 hours of the patient or LAR providing informed consent. The dosing will be based on actual body weight obtained
															

	
at the time of hospitalization or screening for the study, whichever is the most recent weight at randomization.
 
As described in the pharmacy manual, there will be an upper limit of the absolute dose (volume) of Auxora and volume of Placebo that will be administered for patients weighing more than 125kg. The concentration of CM4620 in Auxora is 1.6 mg/kg.

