In the SAD study (CM4620-101), interim non-compartmental pharmacokinetic (PK) analysis indicates that CM4620 likely distributes to three compartments. Plasma concentrations of compound rise steadily during the 4-hour infusion, with T_{max} achieved at the end of infusion (4 hours). After the end of infusion, there is a rapid and prominent distribution phase followed by a prolonged period of residual drug levels. The terminal elimination phase has not yet been fully characterized as it appears to be much longer than was anticipated based on pre-clinical PK data in mouse, rat, dog and monkey. Plasma concentrations during the terminal phase are approximately 5% of C_{max} values and, as indicated above, to date there have been no clinically significant AEs reported during this phase. Plasma exposures, defined by AUC_{0-24h} , appear to be dose-proportional and reached a maximum of 6710 ng* h /mL in Group 5, which is 4.3-fold below the mean AUC_{24h} in monkey at the NOAEL (29,000 ng*hr/mL).

In the MAD study (Table 2) of Auxora (CM4620-102), subjects in the first group were randomized to receive a single dose of active treatment, 0.50 mg/kg, versus placebo for seven consecutive days. Eight healthy subjects were enrolled in the first group, with five receiving active treatment and three receiving placebo. One of the subjects received placebo at the maximum dose volume of emulsion, 1.3 mL/kg, for 7 days, whereas all others were dosed on a weight-based adjustment of dose volume. There were no SAEs and no AEs classified as moderate or severe in intensity. There were 15 clinical AEs that were all classified as mild. In each case, no action was taken with respect to study treatment because of the AEs. No laboratory abnormalities were observed that were considered clinically significant.

Table 2. MAD (CM4620-102)

Group	Active Treatment Daily for 7 days	Number of Active Treatment Subjects	Number of Placebo Treatment Subjects	IV Dose Volume (mL/kg)
1	0.5 mg/kg	5	3	0.3125a
2	1.0 mg/kg	6	2	0.625

^a one placebo patient received maximum dose volume of 1.3 mL/kg

Subjects in the second group of CM4620-102 were randomized to receive a single dose of active treatment, 1.0 mg/kg, versus placebo for seven consecutive days. Eight healthy subjects were enrolled in the second group, with six receiving active treatment and two receiving placebo for seven consecutive days. There were no SAEs and no AEs classified as moderate or severe in

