Fluid from a bronchoalveolar lavage (BAL) should be obtained prior to the SFISD (-12 hours) and then again 24 (± 12) hours after the last infusion of study drug in Cohorts 1 and 2. In Cohort 3, BAL fluid will be obtained during the final 24 hours of the continuous infusion. BAL fluid will be used for flow cytometry, single cell RNA sequencing, and chemokine/biomarker panel. On the BAL fluid obtained from the second BAL, CM4620 levels will be determined in patients receiving Auxora.

ECGs will be performed and the QTcF will be recorded daily at each assessment until 144 (+2) hours from the SFISD. If at any time QT prolongation is suspected on a cardiac monitor, a ECG will be performed and a QTcF shall be recorded. Blood specimen for PK analysis should be obtained in patients receiving Auxora.

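### In Cohorts 1 and 2 no scheduled QTcF is planned near the end of an infusion, the stated time of peak concentration, so the two QTcF criteria that feed escalation have no planned near-peak reading

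*Protocol*

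**What the plan says.** Section 1.4.1 of the protocol reports from the single-dose study that Tmax is "achieved at the end of infusion (4 hours"), and continues: "After the end of infusion, there is a rapid and prominent distribution phase followed by a prolonged period of residual drug levels".

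In Cohorts 1 and 2, "study drug will be administered intravenously as a continuous infusion over 4 hours" (Section 7.5). Infusions start at 0, 24 and 48 hours, and also at 72 hours in Cohort 2.

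On ECGs, Section 3.1 says: "ECGs will be performed and the QTcF will be recorded daily at each assessment until 144" hours. The visit text in Sections 8.5 to 8.10 repeats one line for the 24, 48, 72, 96, 120 and 144 hour assessments: "Perform ECG and record QTcF interval (-2 hours"). Appendix 2 shows the same times and has no QTcF in the 0-hour column. Section 3.1 also requires an unscheduled ECG whenever QT prolongation is suspected on a cardiac monitor.

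Staff already collect a sample at the first peak: "At the end of infusion of Auxora, draw blood sample for PK (+30 minutes"). No ECG is paired with it.

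Section 3.1 of the protocol and the SAP section on interim analysis list five cardiac conduction events within 144 hours that lead to consultation and may lead to cohort expansion. Two are QTcF values: 500 msec or more, and a rise of 60 msec or more from baseline. The other three are Mobitz II block, third-degree or high-grade AV block, and polymorphic ventricular tachycardia. Escalation follows review of safety events.

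**The concern.** If a QTcF effect follows plasma concentration, it is most likely to show at the end of an infusion. The protocol gives that time as the peak but schedules no ECG there in Cohorts 1 and 2. A short-lived rise could meet one of the QTcF criteria and be gone by the next scheduled tracing. Escalation out of Cohort 1 can rest on as few as three Auxora patients, so a single unobserved event matters.

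The monitor-prompted ECG is a partial safeguard only. The protocol gives no criterion for suspicion. Entry requires QTcF of 440 msec or less (Section 4.1), so a rise from 380 to 440 msec would meet the 60 msec criterion while the value stayed within the entry limit.

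Interpretation is affected too. In Cohort 3 the 24 to 96 hour ECGs fall during the continuous infusion, so the same clock time means a different exposure state from Cohorts 1 and 2. Section 10.8 plans exposure-response work with safety data. In Cohorts 1 and 2 no scheduled QTcF coincides with the end-of-infusion PK sample.

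**Working it through.** The plan gives no figure of its own on this point, so the check is timing arithmetic followed by a bound on the remaining concentration.

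**Timing.** Gap = ECG time − (start of last infusion + 4 h). Starts are 0, 24 and 48 h in Cohort 1, and 0, 24, 48 and 72 h in Cohort 2.

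| ECG (h) | Cohort 1 gap (h) | Cohort 2 gap (h) |
|---|---|---|
| 24 | 24 − 4 = 20 | 20 |
| 48 | 48 − 28 = 20 | 20 |
| 72 | 72 − 52 = 20 | 20 |
| 96 | 96 − 52 = 44 | 96 − 76 = 20 |
| 120 | 120 − 52 = 68 | 120 − 76 = 44 |
| 144 | 144 − 52 = 92 | 144 − 76 = 68 |

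Using the full −2 h allowance takes 2 h off each gap, so the shortest becomes 18 h. A further infusion is due at the time of 2 of the 6 ECGs in Cohort 1 (24 and 48 h) and 3 of 6 in Cohort 2 (24, 48 and 72 h).

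**Windows.** With the ±1 h assessment window, the −2 h ECG window and an infusion of 3.5 to 4.5 h, the 24 h ECG falls between 24 − 1 − 2 − 4.5 = 16.5 h and 24 + 1 − 3.5 = 21.5 h after the first infusion ends.

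The order of ECG and second infusion is not fixed. Section 8.5 says "start the infusion of second dose of study drug 24 hours (± 1 hour) from the SFISD", and an infusion begun at 23 h with an ECG at 25 h puts the tracing 2 h into the infusion. The synopsis, like Section 7.5, is wider: "study drug will again be administered at 24 (± 2) and 48 (± 2) hours from the SFISD". With a start at 22 h and an ECG at 26 h, the tracing would fall at 4 h, the end of infusion. The windows allow this; nothing plans it.

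**Concentration at the scheduled ECG.** Section 1.4.1 gives, for 1.0 mg/kg daily in healthy subjects, a Day 7 Cmax of 637 ng/mL (1.4 times Day 1) and a Day 7 AUC over 24 h of 6830 ng·h/mL (2.6 times Day 1).

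- Day 1 Cmax = 637/1.4 = 455 ng/mL. Day 1 AUC = 6830/2.6 = 2627 ng·h/mL.
- Assume a linear rise from zero over 4 h, which has area 2 × Cmax, and a monotone fall afterwards. The 24 h level cannot exceed the 4 to 24 h mean: (2627 − 2 × 455)/20 = 86 ng/mL, and 86/455 = 19% of Cmax.
- For Day 7, assume also that the pre-dose level equals the level 24 h later. The bound is (6830 − 2 × 637)/22 = 253 ng/mL, and 253/637 = 40% of Cmax.
- The 0.5 mg/kg group gives 17% and 31% in the same way. Day 1: Cmax 363/1.6 = 227, AUC 3190/2.6 = 1227, (1227 − 2 × 227)/20 = 39. Day 7: (3190 − 2 × 363)/22 = 112, and 112/363 = 31%.

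Doses here number three or four, so the relevant share probably lies between the Day 1 and Day 7 bounds.

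**The case against.** The case against is substantial, and several parts of it stand.

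- **Peak-time ECG data exist.** Continuous recording in the single-dose study showed no treatment-related QTcF effect at doses up to 2.1 mg/kg. The largest infusion here is 1.25 mL/kg × 1.6 mg/mL = 2.0 mg/kg. This lowers the concern. It does not close it: those were healthy subjects, repeat dosing stopped at 1.0 mg/kg, and the repeat-dose statement excludes only a sustained effect.
- **Escalation mainly raises duration and total exposure.** All three cohorts start with the same 4-hour infusion, and daily ECGs are a sensible way to follow accumulation. That is true, but they do not show what happens at the end of the short infusion, and nowhere do the documents say that an effect would follow Cmax or that it would not.
- **Other safeguards operate.** Three of the five listed events do not depend on a timed QTcF, an unscheduled ECG can be taken at any time, and an independent committee monitors safety. The gap is confined to the two QTcF criteria.
- **The cohort contrast is imperfect.** Cohort 3 also lacks an ECG at the end of its 4-hour initial infusion. Its 120 and 144 h ECGs follow the end of dosing at 100 h. No formal between-arm QTcF test is planned; safety is tabulated.

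A reader might infer that every scheduled QTcF in Cohorts 1 and 2 is a pre-dose trough. The table shows this is so for only 2 of 6 and 3 of 6, and even there the order is inferred, because only the PK draw is worded as preceding the infusion. A reader might also infer that the Tmax statement and the ECG schedule contradict each other. They do not: one describes the drug and the other sets a timetable.

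**Conclusion.** The point holds as a limited design weakness. In Cohorts 1 and 2 no scheduled QTcF targets the end of any infusion. The nearest planned readings come nominally 20 h later (18 h with the allowance), and the rest come 44 to 92 h later in Cohort 1 and 44 to 68 h later in Cohort 2. At peak, the two QTcF criteria rest on monitor suspicion alone.

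The bounds of 19% and 40% of Cmax assume a linear rise, a monotone fall, a stable pre-dose level on Day 7, and that healthy-subject pharmacokinetics at 1.0 mg/kg carry over to ventilated patients given up to 2.0 mg/kg. The timing result needs none of these.

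It would go too far to say that escalation will proceed on a false negative. That requires a QTcF effect that tracks plasma concentration, which the documents do not report. The change is worth making because it is cheap, not because harm has been shown. No dose, threshold or management rule is at issue.

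**What to change.** 1. **Align ECG timing with the Tmax statement** in Sections 8.5 to 8.8 and Appendix 2. The existing dosing-day ECGs in Cohorts 1 and 2 (24 and 48 h, and 72 h in Cohort 2) can be placed at the end of that day's infusion, nominally 28, 52 and 76 h. This adds no tracing. It costs a pre-dose reading on those days, which no stated rule in the protocol uses, and it moves the first scheduled post-dose ECG from 24 to 28 h. It covers two of three peaks in Cohort 1 and three of four in Cohort 2. The first infusion is covered only if one tracing per patient is added alongside the end-of-infusion PK draw in Section 8.4.
2. **State the order of ECG and infusion** at each dosing-day visit.
3. **Reconcile the infusion windows**: ±1 h in Section 8 against ±2 h in the synopsis and Section 7.5. The sponsor must decide which applies.
4. **If the times stay**, have the SAP report QTcF by time since end of infusion, and not compare Cohorts 1 and 2 directly with on-infusion values in Cohort 3. Infusion start and finish times are already recorded. The clock time of each ECG is also needed, and Section 8 does not explicitly ask for it.

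Items 1 to 3 need a protocol amendment. Item 4 needs only a short SAP addition and the ECG time on the case report form.
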